1.1 Overview of the Problem

Thailand is currently experiencing an alarming HIV epidemic among young men who have sex with men (YMSM), particularly those aged 15–29. In Bangkok, HIV prevalence among YMSM aged 18–24 is as high as 31%. The HIV incidence rate in this group is approximately 12%, which is the highest level documented in Asia.^{1,2} These rates far exceed those in high-risk populations in the United States, where even the most at-risk group, Black MSM, has an incidence rate of around 4%.³ Contributing risk factors among Thai YMSM include being paid for sex, having sex at saunas, and living away from family. The HIV prevalence in northeastern provinces like Ubon Ratchathani and Mahasarakham ranges between 10%–25%, which is over ten times higher than the national average. If no effective prevention strategies are implemented, other regions in Thailand may follow the same trajectory as Bangkok.

1.2 Supporting Evidence

Despite the high risk, very few YMSM are accessing HIV testing or care. According to a joint study conducted by the US CDC and the Thai Ministry of Public Health, only 50.3% of MSM in Thailand had ever been tested for HIV. Of those, merely 24.9% returned for their test results.⁴ As a result, only 12.5% actually knew their HIV status.⁵ Our previous research found that 73.3% of YMSM aged 15–19 and 45% of those aged 20–24 had never tested for HIV.⁶ This indicates that current HIV prevention efforts are failing to reach adolescents and young adults, especially in terms of HIV testing and linkage to care. Furthermore, many healthcare providers, including HIV test counselors, lack adequate knowledge of the Continuum of Prevention and Care (CPC), especially regarding the importance of achieving viral suppression, and often perpetuate stigma and discrimination against YMSM. These systemic issues further hinder engagement in HIV prevention and treatment services.

1.3 Rationale for This Study

To address these urgent gaps, the BAAN HUG-M intervention was developed as a community-based, multi-level approach designed to mobilize YMSM, reduce sexual risk behaviors, and improve access to HIV testing and care. Building on the foundation of the original HUG-M model, BAAN HUG-M integrates individual-level behavior change strategies with community mobilization and health system strengthening, with a particular focus on the full Continuum of Prevention and Care (CPC). The intervention seeks to address structural, social, and individual barriers to HIV testing, engagement in care, and achievement of viral suppression among Thai YMSM. Thailand offers a unique and timely opportunity to evaluate this intervention, owing to its existing public health infrastructure, strong community partnerships, and a policy environment conducive to rapid implementation of evidence-based practices. Findings from this study could help shape national HIV strategies and inform similar efforts throughout Asia and beyond.

1.4 Objective

To evaluate the efficacy of Baan HUG-M in decreasing sexual risk behavior; increasing HIV testing to at least biannually; and increasing prompt, sustained engagement in care among YMSM living with HIV by using a longitudinal cohort of YMSM in Ubon Ratchathani and Mahasarakham

2. Study design and methods of data collection

This study aims to evaluate the effectiveness of the Baan HUG-M intervention, a community-based strategy designed to promote HIV prevention and facilitate access to care among young men who have sex with men (YMSM) aged 15 to 29 years. A longitudinal cohort design is employed across two geographic locations: Ubon Ratchathani (intervention site) and Mahasarakham (control site), with a total sample size of 600 participants (300 per site). The follow-up period spans 24 months, with data collection occurring at five time points: baseline and months 6, 12, 18, and 24.

Data collection comprises self-administered surveys completed via the Qualtrics platform⁷ and self-collected biological specimens, including urine samples and rectal swabs, for chlamydia and gonorrhea testing. All specimens will be transported to and analyzed at the Office of Disease Prevention and Control 10 (ODPC 10), located in Ubon Ratchathani Province. Additionally, study data will be linked to the national HIV database maintained by the Ministry of Public Health. To protect participant confidentiality, no personally identifiable information is collected within the survey. Instead, a Unique Identification Code (UIC) is assigned to each participant to enable secure and systematic linkage of data across multiple sources.

2.1 Procedures

2.1.1 Recruitment and Enrollment

Participant recruitment will be conducted over a one-year period using a comprehensive outreach strategy encompassing both online and offline channels to reach young men who have sex with men (YMSM) in two study locations: Ubon Ratchathani and Mahasarakham. The initial target sample size will be 600 participants (300 per province).

Offline recruitment will involve the distribution of QR codes linking to an online screening form. These will be disseminated at public venues and community gathering points frequented by the target population, including local markets, university canteens, schools (through educational sessions on military conscription), shopping centers, and entertainment venues. The research team will also organize community engagement events such as volleyball tournaments, photography contests, and cultural festivals (e.g., Mor Lum folk music events), as well as outreach activities at bars and clubs popular among YMSM. Collaboration with university lecturers, local public health agencies, and public hospitals will support recruitment efforts.

Online recruitment will be conducted through targeted communication campaigns on social media platforms, supplemented by peer-driven outreach activities to increase engagement and visibility among potential participants.

Interested individuals will be required to complete an online eligibility screening form. Those who meet the eligibility criteria will receive detailed study information and complete an initial electronic consent process. A study team member will then follow up to schedule an appointment, during which a comprehensive informed consent discussion will be conducted. Written informed consent and a photocopy of the participant's national identification card will be obtained. Participants will then view a demonstration video on how to self-collect rectal swab specimens, complete the baseline questionnaire, and provide their first set of biological specimens.

2.1.2 Data Collection

Data will be collected at five time points: baseline, and months 6, 12, 18, and 24 of follow-up. At each round, participants will complete self-administered surveys using tablets or smartphones via the Qualtrics platform. A Unique Identification Code (UIC) will be used to longitudinally link participant data across time points. The UIC will consist of the first letter of the province name, followed by an underscore, the first two letters of the participant's last name, and the date of birth in the DDMMYYYY format (e.g., P_AB01012025). To minimize entry errors, local research staff will select the UIC from a predefined list using a forced-choice format.

At each follow-up round, participants will self-collect biological specimens, including urine samples and rectal swabs, for chlamydia and gonorrhea testing. All specimens will be transported under temperature-controlled conditions to the Office of Disease Prevention and Control 10 (ODPC 10) in Ubon Ratchathani for laboratory analysis. Prior to specimen collection, participants will watch a standardized instructional video to ensure correct self-collection procedures.

HIV-related clinical data including the date of the most recent HIV test, HIV status, initiation of antiretroviral therapy (ART), treatment continuity, and viral load results will be extracted from the national HIV database maintained by the Ministry of Public Health using the participant's national identification number. Access to this database will be restricted to the principal investigator and the study statistician to ensure data confidentiality. All data will be stored in encrypted and password-protected formats on secure institutional servers.

2.1.3 Retention and Engagement Strategies

To promote high retention throughout the study period, the research team will implement continuous engagement strategies through digital communication channels, including the LINE application, SMS, and phone calls, as well as peer-led community outreach. The team will maintain regular contact with participants to provide project updates, appointment reminders, and encouragement to take part in each round of data collection. Participants will receive ongoing support throughout their involvement in the study to foster motivation and consistency in completing questionnaires and providing biological specimens. These combined efforts are expected to result in follow-up retention rates of greater than 60% at each follow-up time point.

2.2 Eligibility criteria

Inclusion Criteria:

- Aged between 15 and 29 years
- Currently residing, studying, or working in either Warin Chamrap District or Mueang District of Ubon Ratchathani Province (intervention site), or in Kantharawichai District or Mueang District of Mahasarakham Province (control site)
- Intend to remain in the study area for at least the next three years
- Assigned male at birth
- Self-identify as gay, men who have sex with men (MSM), bisexual, or *toot* (a locally understood term)
- Have engaged in anal sex (insertive or receptive) with a male partner within the past 12 months
- Willing and able to provide informed consent to participate in the study

Exclusion Criteria:

- Aged ≤ 14 years or ≥ 30 years
- Not currently residing, studying, or working in one of the designated study areas
- Planning to move out of the study area within the next three years
- Assigned female at birth
- Self-identify as a woman, transgender woman, or transfeminine individual
- Unwilling to participate in follow-up activities associated with the study

2.3 Consent

2.3.1 Consent Procedures

All participants will provide written informed consent at the time of enrollment. For participants under the age of 18, a waiver of parental consent will be obtained from the ethics committee to protect them from the risk of involuntary disclosure of their sexual orientation or HIV status. Prior to enrollment, participants will receive a study information sheet in advance. On the scheduled enrollment day, the document will be provided again, and participants will have the opportunity to review it with the support of field staff.

To ensure full comprehension of study procedures, multiple formats will be used, including printed materials, instructional videos (e.g., on self-collection of biological specimens), and verbal explanations by trained personnel. Participants will be encouraged to ask questions about any aspect of the study, including the survey process, biospecimen collection, and their right to withdraw at any time. Informed consent will only be obtained after participants demonstrate understanding and express willingness to participate.

Additionally, at each follow-up visit, field researchers will reassess participants' understanding of the study and reconfirm their voluntary participation. This will include obtaining verbal reconfirmation before completing questionnaires and providing biological specimens, to ensure that participants remain informed and continue to consent throughout the longitudinal study.

2.3.2 Withdrawal/discontinuation criteria

Participants could withdraw from the study at any time and for any reason. Withdrawal did not affect the compensation they had already received or their access to HIV-related services. Common reasons for discontinuation included relocation, being unreachable, or unwillingness to continue participation.

2.4 Data analysis

Both descriptive and inferential statistical methods will be employed to evaluate the effectiveness of the Baan HUG-M intervention over the study period. Analyses will compare the intervention group (Ubon Ratchathani) and the control group (Mahasarakham) across demographic variables, behavioral measures, and health-related outcomes associated with HIV and sexually transmitted infections (STIs).

2.4.1 Descriptive Analyses

Baseline demographic, behavioral, and health characteristics of participants will be summarized using descriptive statistics, stratified by study arm (intervention vs. control). Comparisons will be made between the two study sites (Ubon Ratchathani as the intervention site, and Mahasarakham as the control site) to assess initial differences and changes over time. Categorical variables will be presented as frequencies and percentages. Continuous variables will be summarized using means and standard deviations, or medians with interquartile ranges (25th to 75th percentile), depending on data distribution.

2.4.2 Primary and Secondary Outcome Analyses

To evaluate the effects of the intervention over time, Generalized Estimating Equations (GEE) with appropriate link functions will be applied (e.g., logit for binary outcomes and identity for continuous outcomes). The models will include study arm, time (follow-up round), and their interaction to estimate the effect of the intervention across time points. Robust standard errors will be used to account for within-subject correlation due to repeated measurements. For incidence outcomes (e.g., HIV, chlamydia, and gonorrhea infections), person-time will be calculated, and incidence rate ratios (IRRs) with 95% confidence intervals will be reported.

2.4.3 Multiple Comparisons and p-value Adjustment

When multiple comparisons are made, such as in subgroup analyses or secondary outcomes, adjustments to p-values will be considered to control for the risk of type I error. Methods such as Bonferroni correction or false discovery rate (FDR) adjustment will be applied as appropriate.

2.4.4 Statistical Software

All data analyses will be conducted using STATA version 18.0⁸, which is the primary statistical software used by the research team for data management, descriptive analyses, regression modeling, and longitudinal data analysis.

2.5 Assessment and management of risk

This study will be conducted as a low-risk observational cohort study. However, certain survey items such as those related to sexual behavior and HIV status may be considered sensitive. To minimize potential risks, several protective measures will be implemented. All surveys will be administered anonymously, and data will be stored securely using encrypted systems with restricted access, ensuring that no personally identifiable information is collected.

Participants will be informed of their right to skip any question they find uncomfortable and their right to withdraw from the study at any time without any negative consequences. Field researchers will be available throughout the study to provide support, clarify procedures, and address any concerns. Participants will also be referred to mental health or HIV-related services as appropriate.

In addition, participants who are diagnosed with a sexually transmitted infection such as chlamydia or gonorrhea will receive preliminary counseling and will be referred to appropriate healthcare facilities for further examination and treatment, in accordance with Ministry of Public Health guidelines.

Furthermore, a Data and Safety Monitoring Board (DSMB) will be established to oversee the study's risk mitigation strategies and ensure the ongoing protection of participant safety and well-being. The DSMB will also be responsible for monitoring ethical compliance, providing independent review of study procedures, and advising the research team on any necessary protocol modifications to uphold ethical and safety standards throughout the study.

2.6. Data management

Data will be collected using the Qualtrics platform, with force-response enabled for critical items and programmed skip logic applied where appropriate. After data collection, datasets will be exported, cleaned, and processed using STATA.

Participant data across follow-up rounds will be linked using a Unique Identification Code (UIC) and, for data retrieved from the Ministry of Public Health, the national identification number. All personally identifiable information will be protected through double encryption and securely stored on password-protected servers hosted at Mahidol University. Access to these data will be restricted to authorized personnel only, including the Principal Investigator (PI) and designated data managers.

2.7 Recording and reporting of risk events and incidents

In the event that an adverse or risk-related incident occurs during the study, the research team will document and review the incident systematically. Key information such as the nature of the incident, time of occurrence, individuals involved, and any immediate actions taken will be recorded.

The research team will assess the severity of the incident and determine appropriate follow-up measures. Incidents considered serious or potentially affecting the safety and well-being of participants will be promptly reported to the Data and Safety Monitoring Board (DSMB) for independent review and recommendations. Such incidents will also be reported to the Institutional Review Board (IRB) within the required timeframe in accordance with ethical guidelines.

The research team has clear procedures in place to respond to such incidents in a timely, transparent, and appropriate manner. All incident records will be stored securely and treated as confidential. Participants will also be able to report any concerns or discomfort through confidential communication channels available throughout the duration of their participation in the study.

3. Funding

This study is funded by the National Institute of Mental Health (NIMH), under Grants R01MH119015.

4. Monitoring and auditing

The Principal Investigator (PI) will be responsible for overseeing the overall implementation of the study and ensuring adherence to the approved protocol and ethical standards. In addition, two Project Managers will be assigned to supervise and coordinate different study components, with one responsible for the intervention arm and the other for the control group, to ensure fidelity to procedures and consistency across study sites.

Local implementation and data collection activities will be supported by provincial-level advisors, including representatives from provincial hospitals and Provincial Public Health Offices who will assist in monitoring field operations and ensuring data quality in their respective provinces.

A Community Advisory Board (CAB) will be engaged to provide guidance on participant recruitment strategies and the implementation process, ensuring community involvement and cultural appropriateness throughout the study.

Internal monitoring will be conducted regularly by the core study coordination team to verify data accuracy, review informed consent procedures, and ensure compliance with study protocols, including biospecimen handling and confidentiality safeguards.

The Data and Safety Monitoring Board (DSMB) will conduct independent reviews of study progress, risk events, and participant safety data on a scheduled basis. Additionally, representatives from the Institutional Review Board (IRB) or study sponsors may perform audits to assess protocol compliance, ethical conduct, and data integrity.

All findings from monitoring and auditing activities will be recorded, and any deviations from the protocol will be addressed through corrective actions. Reports will be submitted to the IRB and DSMB as required, and follow-up actions will be tracked to ensure continuous quality assurance throughout the study.

5. Publication and dissemination

The findings from this study will be disseminated through a range of channels to ensure impact at both academic and programmatic levels. Results will be published in peer-reviewed journals and presented at national and international conferences to contribute to the scientific knowledge base. All publications will adhere to ethical guidelines, ensuring the confidentiality of participants and transparent reporting of both positive and negative outcomes.

In addition to academic dissemination, the study team will share summary findings with key stakeholders, including local health authorities, service providers, NGOs, and community-based organizations. Plain-language summaries will be prepared where appropriate to enhance accessibility among non-academic audiences, including community members and local decision-makers.

Given the intervention-focused nature of the study, particular attention will be given to engaging multi-sectoral partners in the study areas to support the refinement and potential scale-up of effective components. Collaboration will include government agencies, the public health system, local NGOs, and community networks. These partnerships are intended not only to support the implementation of the intervention but also to foster sustainability and integration into existing systems beyond the research period.

7.3 Statistical Analysis Plan (SAP)

Study Title: Addressing the Continuum of Care Among High-risk Thai Men

ClinicalTrials.gov Identifier (NCT Number): NCT05161689

Document Date: 01/01/2020

1. Introduction

1.1 Objectives of the Statistical Analysis Plan

The primary objective of this Statistical Analysis Plan (SAP) is to prospectively define the analytical framework, statistical methods, and procedures that will be used to analyze data from the clinical study titled “Addressing the Continuum of Care Among High-risk Thai Men”. This SAP is designed to ensure that the analysis is transparent, reproducible, and aligned with the registered study protocol under ClinicalTrials.gov Identifier NCT05161689.

This SAP is intended to:

- Describe the planned analyses for the primary and secondary study objectives
- Specify the statistical techniques and data handling procedures to be used
- Define the analysis populations
- Outline approaches to address missing data, conduct sensitivity analyses, and implement subgroup analyses

1.2 Background and Significance of the Study

This study aims to evaluate the efficacy of the BAAN HUG-M intervention in:

- Reducing sexual risk behaviors
- Increasing the frequency of HIV testing (at least biannually)
- Promoting prompt and sustained engagement in HIV care

The study is conducted through a longitudinal cohort of young men who have sex with men (YMSM) (“YMSM Cohort”, $N = 600$) residing in Ubon Ratchathani (intervention site) and Mahasarakham (control site). Given the disproportionate burden of HIV among YMSM in Thailand, and the structural and behavioral barriers to care, this study addresses a critical public health challenge with implications for national HIV policy and intervention programming.¹⁻³

2. Study Design Overview

This will be a prospective, longitudinal cohort study involving 600 young men who have sex with men (YMSM) aged 15–29 years, with equal allocation to two study sites:

- Intervention city: Ubon Ratchathani ($n = 300$)
- Control city: Mahasarakham ($n = 300$)

Participants will be followed for 24 months, with data collection scheduled at five time points: baseline, 6 months, 12 months, 18 months, and 24 months.

Data Collection and Sources

Data will be collected through online self-administered questionnaires hosted on the Qualtrics platform and completed using tablets or smartphones. To ensure anonymity while enabling longitudinal data linkage, no personal identifiers will be recorded. Instead, participants will enter a Unique Identification Code (UIC) at each round of data collection.

Retention and Follow-up

To promote high retention throughout the study period, the research team will implement continuous engagement strategies via digital platforms and peer-led community outreach. These efforts are expected to result in follow-up retention rates of greater than 60% at each follow-up time point.

3. Study Objectives and Endpoints

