3.1 Primary Objective

To evaluate the effectiveness of the BAAN HUG-M intervention in increasing access to and engagement with the intervention activities, and in promoting HIV testing uptake among young men who have sex with men (YMSM) who have never previously been tested for HIV.

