3.3 Primary Outcome

- **HIV testing uptake:**

Proportion of participants who report having ever tested for HIV during the 24-month follow-up period. Data will be collected from HIV testing records provided by the Ministry of Public Health national database.

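### Testing at least twice a year is a stated aim, but no planned outcome measures testing frequency

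*Combined protocol and SAP*

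**What the plan says.** The testing aim appears in three forms.

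- **Frequency.** Protocol 1.4 gives one of its aims as "increasing HIV testing to at least biannually". SAP 1.2 repeats it: "Increasing the frequency of HIV testing (at least biannually".
- **Uptake in the never-tested.** The testing part of the primary objective in SAP 3.1 is "promoting HIV testing uptake among young men who have sex with men (YMSM) who have never previously been tested for HIV".
- **Any test, in everyone.** The primary outcome in SAP 3.3 is "Proportion of participants who report having ever tested for HIV during the 24-month follow-up period", without the never-tested restriction. On the source it says: "Data will be collected from HIV testing records provided by the Ministry of Public Health national database".

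The secondary objectives and outcomes (SAP 3.2 and 3.4) cover HIV incidence, chlamydia and gonorrhea, condomless anal intercourse, HIV care, viral load and PrEP. None concerns testing. The outcome analyses (protocol 2.4.2, SAP 6.2) and the subgroup and sensitivity sections (SAP 7.1 and 7.2) define no number of tests, no interval between tests and no per-round testing indicator.

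Among the registry data, protocol 2.1.2 names "the date of the most recent HIV test". Follow-up is 24 months, with rounds at baseline and months 6, 12, 18 and 24 (SAP 2).

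**The concern.** An aim stated in both the protocol and the SAP has no outcome that answers it. A man tested once in two years and a man tested every six months are both full successes under SAP 3.3. A positive primary result would show that more men had at least one test. It would not show that men tested twice a year, and a reader of protocol 1.4 could easily take it that way. Any frequency analysis added later would be post hoc, because its definition, denominator and extraction dates are not fixed now.

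The disagreement between SAP 3.1 and SAP 3.3 is a related gap. The primary objective and the primary outcome have different denominators, and the plan does not say which governs.

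**Working it through.** The documents give 600 participants (300 per site) but no expected testing rate, effect size, alpha or power for the testing outcome. There is no figure to reproduce. The central check is the comparison of aim and outcomes above; the arithmetic shows how far the two measures can differ.

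**Required tests.** Twice a year over 24 months is 2 × 2 = 4 tests. SAP 3.3 requires 1.

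**Assumptions (not from the documents).** Biannually means twice a year. Each man tests at a constant random rate of *r* per year (Poisson), independently across windows.

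- Any test in 24 months: 1 − exp(−2r)
- Test in a given 6-month window: w = 1 − exp(−r/2)
- Test in all four windows: w⁴
- Mean number of windows with a test: 4w

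| r per year | Any test | w | All four windows | Mean windows (of 4) |
|---|---|---|---|---|
| 0.25 | 39% | 0.118 | 0.02% | 0.47 |
| 0.5 | 63% | 0.221 | 0.24% | 0.88 |
| 1 | 86% | 0.393 | 2.4% | 1.57 |
| 2 | 98% | 0.632 | 16% | 2.53 |

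For r = 1: 1 − exp(−2) = 0.865, and (1 − exp(−0.5))⁴ = 0.393⁴ = 0.024.

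**Would each measure detect a doubling of the rate?** Two-sided alpha 0.05, normal approximation, ignoring that each arm is a single city. The arm sizes are 300 and, at 60% retention, 0.6 × 300 = 180. For proportions, power = Φ[(|p₂ − p₁| − 1.96·SE₀)/SE₁], with SE₀ pooled and SE₁ unpooled. For the window count, power = Φ[4(w₂ − w₁)/SE − 1.96], with SE = √{[4w₁(1 − w₁) + 4w₂(1 − w₂)]/n}.

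| Change in r | n per arm | Any test | All four windows | Window count |
|---|---|---|---|---|
| 0.25 to 0.5 | 300 | >99.9% | 11% | >99.9% |
| 0.25 to 0.5 | 180 | 99.6% | 8% | >99.9% |
| 0.5 to 1 | 300 | >99.9% | 64% | >99.9% |
| 0.5 to 1 | 180 | >99.9% | 43% | >99.9% |
| 1 to 2 | 300 | >99.9% | >99.9% | >99.9% |
| 1 to 2 | 180 | 98.8% | 99.5% | >99.9% |

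Worked case, any test, 1 to 2 a year, 180 per arm: (0.117 − 1.96 × 0.0281)/0.0274 = 2.26, and Φ(2.26) = 98.8%.

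The window-count figures assume independent windows; correlation within a man lowers them. In the extreme where all four windows agree, SE for the mean of w is √{[w₁(1 − w₁) + w₂(1 − w₂)]/n}. For 0.25 to 0.5 a year and 300 per arm this is √(0.276/300) = 0.0303. Power is then Φ(0.104/0.0303 − 1.96), about 93%. With 180 per arm it is about 75%.

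The any-test outcome is therefore sensitive to a change in rate, but its level says little about twice-yearly testing. The all-four-windows proportion matches the aim most literally but sits near zero when testing is rare. The window count follows frequency without that floor.

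**The case against.** A reader might infer two stronger claims, and the documents support neither.

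*That the trial cannot answer the aim at all.* This goes too far. Protocol 2.1.2 opens with collection at five time points, and its registry list is introduced as examples: "HIV-related clinical data including the date of the most recent HIV test, HIV status". SAP 3.3 refers to testing records. SAP 3.4 takes retention in care at months 6, 12, 18 and 24, and viral load at each round, from the same database. Round-by-round registry data are therefore evidently intended, and a most-recent-test date read at each round would give a tested-in-this-window indicator. The gap lies in the pre-specified outcomes and analyses, not necessarily in the data.

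*That the any-test outcome would reach its ceiling and miss a real rise in frequency.* Every doubling checked above is detected with power of at least 98.8%. Protocol 1.2 also describes a population in which testing is uncommon: 50.3% of MSM ever tested, and 73.3% of those aged 15–19 and 45% of those aged 20–24 never tested. One can construct a case with equal any-testing and unequal frequency, but nothing in the documents makes it the expected one.

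It is also fair to say that a binary uptake outcome is a legitimate match to the uptake wording of SAP 3.1, and that the frequency aim in the SAP stands in its background section. But the same aim is in the protocol's objective, and SAP 1.1 undertakes to align the analysis with the protocol. The absence of any frequency outcome stands.

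**Conclusion.** The point holds in a limited form. Followed exactly, the plan does not evaluate the aim of testing at least twice a year, because its only testing outcome counts one test in 24 months as a full success. On the assumed constant rates, men testing once a year would give 86% on the SAP outcome while 2.4% tested in every 6-month window. The percentages rest on the Poisson assumption and on reading biannually as twice a year, which the documents do not define; the mismatch between aim and outcome does not depend on the chosen rates. The any-test result remains valid for its narrower question. This should be corrected, but it does not invalidate the primary outcome.

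The conflict between SAP 3.1 and SAP 3.3 is separate and needs its own resolution. A reader might infer that the primary analysis must be cut to never-tested men. The documents do not settle that. If the 50.3% ever-tested figure in protocol 1.2 applied, the cut would remove about 0.503 × 600 = 302 participants.

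**What to change.** 1. Define biannually in protocol 1.4 and SAP 1.2.
2. State that the registry linkage will extract all dated HIV tests through month 24 or, failing that, the most recent test date at every 6-month round. The full list is safer: if a pull is late, a newer test can replace the one that belonged to the window.
3. Add a secondary outcome to SAP 3.4: the number of 6-month windows (0 to 4) with at least one registry test. Analyse it as a tested/not-tested indicator per window in the GEE already planned (arm, time and their interaction), among participants not known to be HIV-positive at the start of that window.
4. Report the proportion tested in all four windows descriptively only, because of the floor shown above.
5. Reconcile SAP 3.1 with SAP 3.3. Keeping the outcome in all participants, and adding never-tested men as a pre-specified subgroup in SAP 7.1, avoids losing sample from the primary analysis. This needs each man's pre-baseline testing status.

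If the sponsor does not want a frequency outcome, the alternative is to restate the aim as any testing.

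The cost is a few more fields from a linkage already planned, some SAP wording, and one more secondary outcome under the multiplicity adjustment in SAP 6.3.
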